2.4 Correlative Studies

- **PD-L1/L2 Expression**

The current understanding on whether PD-L1 and PD-L2 status is a biomarker of response is limited, as there are no published data on frequency of PD-L1/L2 expression in western populations and there is no uniformly accepted readily available validated assay. To test the hypothesis that PDL-1/L2 status correlates with outcome, pre-and post-treatment formalin-fixed, paraffin-embedded (FFPE) tissue will be evaluated using the validated assay by Merck. As ligand status was not tested in all patients in prior trials and, some PD-L1 / L2 + patients failed to respond, we as yet do not know if this should be an exclusion criterion. In patients whose tumors are PD-L1 / L2 positive before therapy commences and they do NOT respond to combination treatment, then an optional second biopsy will be performed to test our hypothesis that there may be a change in their PD-L1 / -L2 expression status.

- **Immune Biomarkers**

Determining immune marker changes that can predict clinical benefit and toxicities (as some of them may have an immune basis) would be valuable to the clinician. To this end we propose to address our hypothesis that sorafenib+anti-PD-1 treatment will diminish checkpoint blockade and the accumulation of immunosuppressive networks in advanced stage HCC patients and thereby restore beneficial cytotoxic anti-tumor function in effector T cells. We will assess the alteration in the frequency and phenotype of immunosuppressive cells prior to treatment and, importantly, at three additional time points after commencement of the combination. In addition, the activity of the NFAT transcription factor which regulates PD-1 expression in these cells will be assessed. A longitudinal study of this nature is ideal to determine the kinetics and maintenance of sorafenib and anti-PD1 mediated immunomodulation.

Baseline levels of immunosuppressive cells and the functional activity of effector T cells as measured by NFAT activity, proliferative capacity and IFN-gamma and granzyme B production will be correlated with OS to determine whether these could serve as biomarkers and identify patients most likely to benefit from the combination therapy.

- **Immune-Mediated Adverse Events:**

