11.3 Pathology

11.3.1 Pre-treatment Formalin-Fixed Paraffin-Embedded (FFPE) Biopsy Samples

The following sections of tissue from the most recent (or available) liver biopsy (neoplastic tissue) that exists in the Paraffin Archive in the Department of Pathology (or outside institution) will be collected if available:

1. Eight unstained sections cut at 4 microns on plus glass slides:
 - a. Four (4) for PD-L1/-L2 testing (RPCI Pathology Resource Network for analysis)
 - b. Four (4) for Nanostring analysis (RPCI Genomics Shared Resource for analysis).
2. One H&E stained section (RPCI Pathology Resource Network).

Roswell Park Protocol No.: I 35316

3. Five (5) unstained sections cut at 4-micron thickness on Fisher ProbeOn Plus slides for PD-L1 testing (QualTek). Refer to *QualTek MISP Sample Handling Manual* for detailed processing and shipping instructions. **NOTE: ALL SITES will send these samples DIRECTLY to QualTek.**

NOTE: If a fresh pre-treatment liver biopsy is obtained as a part of standard of care:

- *1 core*: Fixed in formalin for 8 to 24 hours and processed as paraffin embedded block (FFPE block)
- Section as per Section 11.3.1 prior to shipment

For **External (Network) Sites**, the de-identified tissue samples should be labeled using study-specific subject ID number and tissue accession#. All of the above slides and/or block (*except the slides to QualTek*) are to be sent to RPCI Correlative Science Pathology Office (Attn: Protocol Lab Team). Please ship slides ambient (or with a refrigerated gel pack when temperatures will exceed 24°C). The **shipping label** should read as follows:

Roswell Park Cancer Institute
[name]
Correlative Science Pathology Office
Gratwick Basic Science Building, S-636
Attn: Protocol Lab Team, I 35316 Samples
[name]
[contact]

Email: [contact]

Samples for NanoString analysis (4 unstained slides) will be batched and sent from the CSPO to [name], Assistant Director Genomics Shared Resource, CGP & COE L1-210, for analysis. For additional information regarding the handling of samples please contact [name] at [contact] (office) or email [contact].

Samples for PL-L1/-L2 testing (4 unstained slides and 1 H&E) will be batched and sent from the CSPO to [name], GBSB-S608, for analysis. For additional information regarding the handling of samples please contact [name] at [contact] (office) or email [contact].

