11.3.2 Post-treatment Liver Biopsy Samples

PD-L1,-L2 positive patients will be asked to undergo an *optional*, post-treatment biopsy for PD-L1,-L2 at the end of treatment, to assess any change in ligand status (6 responders to treatment and 6 non-responders).

Optional Post-Treatment Biopsy Tissue Requirements

Four (4) cores each from tumor and adjacent normal liver tissue:

- *3 cores each of tumor and adjacent normal liver tissue* (each core to be stored separately): Snap frozen in cryovials in liquid nitrogen for subsequent RNA/DNA analysis (2 cores each) and future biomarker studies (1 core each).
- *1 core each of tumor and adjacent normal liver tissue*: Fixed in formalin for 8 to 24 hours and processed into separate paraffin embedded blocks (FFPE blocks) for subsequent CYTOF and PD-L1/L2 analysis

All of the above tissue samples will be sent to RPCI Correlative Science Pathology Office (Attn: Protocol Lab Team). The shipping label should read as follows:

Roswell Park Cancer Institute
[name]
Correlative Science Pathology Office
Gratwick Basic Science Building, S-636
Attn: Protocol Lab Team, I 35316 Samples
[name]
[contact]

Email: [contact]

For External (Network) Sites: Follow directions above for sample collection, processing and, shipping. The cryogenic tubes FFPE blocks are to be labeled with the clinical study number and patient study ID, collection date/study cycle and day and, “Tumor” or “Adjacent Normal Liver”. Snap-frozen samples are to be batch-shipped frozen, on dry ice. FFPE blocks may be batch-shipped at ambient temperature (please include refrigerated gel pack when temperatures will exceed 24°C).

Frozen samples will be shipped via Fed Express Overnight on dry ice with delivery on Mon-Fri. NO SATURDAY DELIVERY. Do not ship on a Friday or the day before a holiday.

11.3.3 PD-L1/L2 and CYTOF analysis of Post-treatment Formalin-Fixed Paraffin-Embedded (FFPE) Biopsy Samples

At RPCI, the following sections will be prepared from the post-treatment biopsy FFPE blocks:

1. Eight unstained sections of each sample (tumor and adjacent normal liver) cut at 4 microns on plus glass slides (4 of each sample for PD-L1/-L2 testing to RPCI Pathology Resource Network for analysis, 4 of each sample for Nanostring analysis).
2. Two H&E stained sections (1 from each block).

Roswell Park Protocol No.: I 35316

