3. Five (5) unstained sections (tumor tissue only) cut at 4-micron thickness on Fisher ProbeOn Plus slides for PD-L1 testing (QualTek). Refer to QualTek MISP Sample Handling Manual for detailed processing and shipping instructions.

Once all sections from the FFPE core have been taken, the remainder of the blocks will be sent to RPCI Immune Analysis facility (c/o [name]) for CYTOF analysis.

Samples for NanoString analysis (FFPE sections) and the snap-frozen samples for RNA/DNA analysis and biomarker analysis will be sent from the CSPO to [name], Assistant Director Genomics Shared Resource, CGP & COE L1-210, for analysis. For additional information regarding the handling of samples please contact [name] at [contact] (office) or email [contact]

Samples for PL-L1/L2 testing (4 unstained slides of each sample and 1 H&E of each sample) will be sent to RPCI's Core Pathology Laboratory for analysis.

Note: All investigator or analyzing research laboratories housing research samples need to maintain current **Temperature Logs** and study-specific **Sample Tracking and Shipping Logs**. The Principal Investigator/Laboratory Manager **must** ensure that the stated lab(s) have a process in place to document the receipt/processing/storage/shipping of study-related samples/specimens. This is required for both observational and interventional clinical studies collecting clinical samples.

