19.4 Correlative Data Analysis

Measurements for several immune parameters will be obtained before and after treatment. The effect of treatment will quantified as the post/pre-treatment mean ratio of the (potentially log transformed) expression measurements. Primary and derived immune marker expression measurements will be summarized with common descriptive statistics (mean / standard deviation). Associations between the paired pre- and post-measurements will be described with scatterplots and dot plots. The null hypothesis of no difference in the paired pre- and post-treatment measurements was assessed using permutation paired t-tests.

In previous experiments, immune marker expression measurements varied widely, with means between 8.0 and 1,200; the coefficient of variation has been between 0.5 and 1.0. For power calculations, the (original scale) expressions are assumed to have mean (standard deviation) of 100 (100), and within-patient correlation = 0.20. Comparing measurements at two time points, the within-patient effect of therapy on an immune marker can be assessed using a permutation paired t-test. A paired t-test with a two-sided significance threshold of 0.05 has 80% power to

Roswell Park Protocol No.: I 35316

detect a fold-change of at least 1.76 in the post/pre geometric means.

All data analyses were generated using SAS/STAT software, Version 9.4. Copyright 2012, SAS Institute Inc. SAS is a registered trademark of SAS Institute Inc., Cary, NC, USA.

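### If the paired pre/post test in 19.4 is applied to tumour PD-L1/L2, selecting patients on a positive pre-treatment result biases the comparison towards loss of ligand

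*Combined protocol and SAP*

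**What the plan says.** **Who is re-biopsied.** Section 11.3.2 restricts the optional second biopsy to ligand-positive patients. It describes it as a "post-treatment biopsy for PD-L1,-L2 at the end of treatment, to assess any change in ligand status", with 6 responders and 6 non-responders. Section 2.4 is narrower: "In patients whose tumors are PD-L1 / L2 positive before therapy commences and they do NOT respond to combination treatment", an optional second biopsy tests whether expression status has changed. Neither section plans a second biopsy for ligand-negative patients.

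**What the baseline is.** Under 11.3.1 the pre-treatment tissue is taken, if available, "from the most recent (or available) liver biopsy (neoplastic tissue) that exists in the Paraffin Archive". Its age is not fixed. Sections go both to the RPCI pathology laboratory (PD-L1/L2) and to QualTek (PD-L1). Section 11.3.3 does the same for post-treatment tissue.

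**How change is analysed.** Section 19.4 opens: "Measurements for several immune parameters will be obtained before and after treatment". It takes the treatment effect to be the "post/pre-treatment mean ratio of the (potentially log transformed) expression measurements" and names one test: "The null hypothesis of no difference in the paired pre- and post-treatment measurements was assessed using permutation paired t-tests". Its power statement assumes mean 100, SD 100 and within-patient correlation 0.20, and gives 80% power for a 1.76-fold change. Section 19.3 treats any p-value below 0.05 as significant, without adjustment for multiple testing. Nothing in either section deals with selection on the baseline value.

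**The concern.** A permutation paired t-test builds its reference distribution by flipping the signs of the within-patient differences. That is valid only if pre and post are interchangeable when treatment has no effect. Here a pair exists only because the pre value passed a positivity threshold, and the post value passed no such filter. Unless the within-patient correlation is 1, post values will on average be lower with an inert treatment. For the ligand used for selection, a patient can only stay positive or become negative.

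The bias produces an apparent change in ligand status, which is the hypothesis of 2.4, and it would offset a true rise. Because 19.4 calls the post/pre ratio the effect of treatment, a fall due to regression to the mean could be reported as a drug effect on the tumour.

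**Working it through.** **Inputs from the plan.** CV = 100/100 = 1; original-scale correlation 0.20; two-sided 0.05 (19.4). Up to 6 + 6 = 12 pairs (11.3.2). 27 evaluable patients and target ORR 0.20 (19.1).

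**Assumptions, because the documents give no figure.** Proportion of tumours positive 20%, 50% or 80%; biopsy uptake 100% or 50%; log-normal marker; response unrelated to ligand level.

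**Step 1: reproduce the plan's figure.**
- Log SD = √ln(1 + 1²) = 0.8326.
- Log-scale correlation = ln(1.20)/ln 2 = 0.263.
- SD of the paired log difference = 0.8326 × √(2 × (1 − 0.263)) = 1.011.
- Solving noncentral-t power for 80% gives a fold-change of 1.761 at n = 27, which matches the stated 1.76. At n = 12 it is 2.455.

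So the log-normal model fits the plan's calculation, and that calculation is for 27 pairs, not for 12 biopsies.

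**Step 2: expected ratio with no treatment effect.** Let P be the proportion positive, c the matching standard normal cut-off and ρ the log-scale correlation. Then ratio = exp(−(1 − ρ) × 0.8326 × φ(c)/P). At ρ = 0.263 the multiplier is 0.737 × 0.8326 = 0.6136.
- P = 20%: φ(c)/P = 1.400; exp(−0.859) = 0.42.
- P = 50%: φ(c)/P = 0.798; exp(−0.490) = 0.61.
- P = 80%: φ(c)/P = 0.350; exp(−0.215) = 0.81.

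At ρ = 0.5 the ratios are 0.56, 0.72 and 0.86; at ρ = 0.8 they are 0.79, 0.88 and 0.94.

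**Step 3: status change with no treatment effect.** The proportion of positives that read negative on re-biopsy is 1 − Φ₂(−c, −c; ρ)/P. At P = 50% and ρ = 0.263 this is 1 − (0.25 + arcsin(0.263)/2π)/0.5 = 0.415. At 20% and 80% positivity it is 0.69 and 0.17.

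**Step 4: false rejection at nominal 5%.** Simulated with no true change, pairs kept only if the pre value is positive, and all sign flips enumerated. Repeat runs agree to within a few percentage points.

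| Setting | 20% positive | 50% positive | 80% positive |
|---|---|---|---|
| 12 complete pairs, ρ = 0.263 | 90% | 40% | 11% |
| 12 complete pairs, ρ = 0.5 | 70% | 28% | 9% |
| 12 complete pairs, ρ = 0.8 | 30% | 13% | 7% |
| 27 patients, ORR 0.20, caps 6 + 6, full uptake, ρ = 0.263 | 24% | 27% | 9% |
| As above, half uptake | 2% | 13% | 7% |
| Non-responders only (cap 6), full uptake, ρ = 0.263 | 9% | 13% | 4% |

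Without selection, 12 pairs reject in about 5% of trials, with ratio 1.00. With 12 selected pairs at ρ = 0.263, almost all rejections are towards loss.

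**Step 5: why the first three rows are upper bounds.** At ORR 0.20, 27 patients yield 27 × 0.20 = 5.4 responders, of whom 2.7 are ligand-positive at 50% positivity. At 20% positivity only 27 × 0.20 = 5.4 patients are positive in total, and the chance of at least 12 is 0.4%. With 5 pairs the smallest possible two-sided p-value is 2/32 = 0.0625, so the test cannot reject.

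**The case against.** **Section 19.4 may not be meant for the ligands.** It does not name PD-L1/L2, its power figure fits 27 pairs, and 2.4 lists ligand expression and immune biomarkers under separate headings. Change in status is categorical, and 19.3 offers Fisher's exact test for categorical data. This stands in part: the test's use on the ligands is a reading, not a statement of the plan. But 19.4 is the correlative analysis section and contains the only pre/post method. If it does not apply, a stated hypothesis that uses an invasive biopsy has no analysis. Either way text is needed.

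**A reader might infer that an inert treatment would probably appear to confirm loss of ligand.** The documents do not support that. The 90% and 40% rates need 12 complete pairs, which 27 patients with an ORR of 0.20 are unlikely to supply at 20% positivity, and the biopsy is optional. With attainable numbers no cell exceeds about 27%, and for the non-responders of 2.4 none exceeds about 13%.

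**A reader might also infer that status can only be lost.** That holds only for the ligand used for selection. Positivity is not defined. If either ligand qualifies, a PD-L1-positive, PD-L2-negative patient could gain PD-L2.

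**The sub-study is exploratory and small.** True, and this limits the importance of the point. It does not justify a test whose error leans towards its own hypothesis.

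**Conclusion.** The concern holds conditionally. If the 19.4 test and ratio are applied to the ligand on which patients were selected, the estimate is biased towards loss whatever the number of pairs, and the null distribution is wrong. The ratio under no effect is about 0.42 to 0.81 at the plan's CV and correlation, over an assumed 20% to 80% positivity, and closer to 1 if repeatability is better. False rejection is moderately raised with attainable pairs and full uptake (about 9% to 27%). At half uptake it ranges from about 2% to 13%, and it falls below 5% where there are too few pairs to reject.

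The size depends on positivity rate, cut-off, repeatability and uptake, none of which the documents give. The blood markers are not selected on baseline positivity and are not affected, nor are the primary and secondary endpoints. The point should be corrected, but it is confined to the ligand-change analysis.

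**What to change.** In 19.4, state that the permutation paired t-test and the treatment-effect reading of the post/pre ratio are not applied to tumour PD-L1/L2 in patients selected on a positive pre-treatment result. In their place:

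- Report the number changing status with an exact confidence interval, descriptively, and do not attribute a fall to treatment. This needs a stated definition of positivity for each ligand.
- For PD-L1, show beside it how often the RPCI and QualTek reads disagree on the same pre-treatment tissue. This is a reference for assay error only; it does not cover variation from block age, sampling or biology.
- If responders are also biopsied as in 11.3.2, compare change between responders and non-responders. This largely cancels the bias, provided pre-treatment levels and repeatability are similar in the two groups. It will be imprecise, with about 2.7 positive responders expected at 50% positivity.
- Reconcile 2.4 and 11.3.2 on who is re-biopsied. Under 2.4 as written there are no responders to compare.

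The analysis changes need only SAP wording. The cost is that the ligand-change result becomes descriptive and supports a weaker claim. Two other remedies are less attractive. Using one laboratory's read to select and the other's as baseline removes only assay error and alters who is offered a biopsy. Offering the biopsy regardless of ligand status removes the selection, but is a protocol change that extends an invasive procedure to ligand-negative patients.

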20.0 Provisions to Monitor the Data to Ensure the Safety of Subjects

Phase 1 studies will be reviewed at the scheduled RPCI Phase 1 meetings and the minutes are forwarded to the IRB for review.

Phase 2 studies: The RPCI Data and Safety Monitoring Board will assess the progress of the study, the safety data, and critical efficacy endpoints. The DSMC will review the study annually and will make recommendations that include but not limited to; (a) continuation of the study, (b) modifications to the design, (c) suspension of, or (d) or termination of the study.

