9.0 Design

This is an open-label, single arm, non-randomized, multi-center Phase Ib/II study of sorafenib when administered with pembrolizumab in patients with advanced hepatocellular carcinoma. The study will include an initial Phase Ib safety lead-in cohort of 6 patients.

Prior to starting on the combination therapy of sorafenib + pembrolizumab, patients will have completed initial treatment with sorafenib alone and must be stable on sorafenib (at least 200 mg BID for a minimum of 1 week) before the introduction of pembrolizumab. The sorafenib starting dose will be at the discretion of the treating physician based on clinical assessment of the patient.

All participants will sign an informed consent prior to any study-related tests. All participants will meet the inclusion and exclusion criteria summarized in Section 3.1 and 3.2.

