9.1 Phase Ib/II

The first 6 patients who have completed at least 4 weeks of sorafenib-only treatment and begin the combination therapy (addition of pembrolizumab at a fixed dose of 200 mg Q3W) will comprise the Phase 1b safety lead-in. Patients who withdraw from the study prior to initiation of combination therapy (for reasons other than DLT) will be replaced.

Definition of Dose-Limiting Toxicity: A dose-limiting toxicity will be defined as any \geq grade 3 clinically significant toxicity which is deemed possibly treatment related and occurs within the first cycle of combination therapy. Toxicity will be assessed according to the NCI Common Terminology Criteria for Adverse Events [Version 4.0 \(CTCAE v4.0\)](#).

Patient data for the safety lead-in portion of the study will be discussed and monitored by The Early Phase Clinical Trials committee, which meets on a regular basis per the RPCI Data Safety Monitoring Plan.

After a minimum of 6 have completed at least one cycle of sorafenib + pembrolizumab, the study will be suspended, and the safety/tolerability of the combination will be examined. At that time, the study team will decide what action to take, e.g., continue the study as is, make changes to the study with regard to treatment or dose modifications, or discontinue the study.

- If ≥ 2 of these patients experience an unexpected, treatment related toxicity of grade ≥ 3 during the first cycle of combination therapy, the study will be stopped to reevaluate dosing. We anticipate that such limiting toxicities will be observed in ≤ 1 of the first 6 patients. All evaluable patients who receive the Phase 2 dose of pembrolizumab (200 mg Q3W) will be included in the Phase 2 study.

Once analysis is complete and a safe treatment plan has been established, the Phase II study will commence.

Patients who have toxicity during the first 3 weeks of combination therapy that appears to be attributed to sorafenib will have sorafenib dose reduced to 2 x 200 mg every other day, as was done in the SHARP study(11). We anticipate such dose modifications to be infrequent. Patients will be considered evaluable if they receive more than 75% of prescribed sorafenib dosing during

Roswell Park Protocol No.: I 35316

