10.0 Treatment

Dosing and Administration

1 cycle = 3 weeks of combination therapy

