10.2 Pembrolizumab

Starting with Cycle 1, treatment with pembrolizumab will be administered on Day 1 of each 3-week treatment cycle, after all procedures and assessments have been completed (as detailed on the Schedule of Procedures: Appendix E).

Pembrolizumab will be administered at a fixed dose of 200 mg, using a 30-minute IV infusion. Sites should make every effort to target infusion timing to be as close to 30 minutes as possible. However, given the variability of infusion pumps from site to site, a window between -5 minutes and + 10 minutes is permitted (i.e., infusion time is 30 minutes -5 min and + 10 min).

The Pharmacy Manual contains specific instructions for the preparation of the pembrolizumab infusion and administration of infusion solution.

Toxicities will be assessed upon completion of the first 6 evaluable patients to see if any higher than anticipated occurrence of sorafenib toxicity is seen due to the addition of pembrolizumab.

Reported adverse events (AEs) and potential risks are described in Section 13. Appropriate dose modifications are described in Table 1 (see **Appendix F**).

Pembrolizumab Dose Modifications

Adverse events (both non-serious and serious) associated with pembrolizumab exposure may represent an immunologic etiology. These adverse events may occur shortly after the first dose or several months after the last dose of treatment. Pembrolizumab must be withheld for drug-related toxicities and severe or life-threatening AEs as per Table 1 (**Appendix F**).

Dosing interruptions are permitted in the case of medical / surgical events or logistical reasons not related to study therapy (e.g., elective surgery, unrelated medical events, patient vacation, and/or holidays). Participants should be placed back on study therapy within 3 weeks of the scheduled interruption. The reason for interruption should be documented in the patient's study record.

Management and dose modifications associated with the above AEs are outlined in **Appendix F**.

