19.1 Sample Size Determination

Proposed is a one-stage, single arm, unblinded Phase II trial. ORR for patients receiving the standard of care therapy is around 0.05. An exact one-stage design proposed by Kepner and Chang tests the null hypothesis that the proposed treatment has an ORR that is equal to the

Roswell Park Protocol No.: I 35316

standard of care, against an alternative that it is greater. The design has 80% power to detect an ORR of 0.20 or greater with the study treatment, while controlling to 5% the nominal probability of erroneously finding a truly ineffective treatment as worthy of further research (21, 22).

The first 6 patients will comprise the Phase 1b safety lead-in. If ≥ 2 of these patients experience an unexpected, treatment related toxicity of grade ≥ 3 during the first cycle of therapy, the study will be stopped to reevaluate dosing. We anticipate that such limiting toxicities will be observed in ≤ 1 of the first 6 patients. All evaluable patients who receive the Phase 2 dose will be included in the Phase 2 study.

We expect 27 evaluable patients will be enrolled on the trial. If 4 or more of the 27 evaluable patients achieve complete or partial response, the treatment will be deemed effective and considered for further study.

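### After the 2-of-6 lead-in check, no study-level toxicity count applies in Phase II, and the event that the check counts does not match the dose-limiting toxicity definition

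*Combined protocol and SAP*

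**What the plan says.** Section 9.0 announces the lead-in: "The study will include an initial Phase Ib safety lead-in cohort of 6 patients". Section 19.1 repeats it: "The first 6 patients will comprise the Phase 1b safety lead-in". Under Sections 9.1 and 19.1, if 2 or more of these patients "experience an unexpected, treatment related toxicity of grade" 3 or higher in the first cycle, "the study will be stopped to reevaluate dosing". Section 10.0 fixes the window: "1 cycle = 3 weeks of combination therapy". The sponsor expects at most 1 such patient in 6.

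Section 9.1 defines a dose-limiting toxicity differently, as a grade 3 or higher "clinically significant toxicity which is deemed possibly treatment related and occurs within the first cycle of combination therapy". That definition does not require the event to be unexpected. Section 17.1 treats an event as unexpected when the investigator brochure does not list it, or does not list it at the observed specificity or severity.

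Section 9.1 also suspends the study, whatever the count, once at least 6 patients have completed a combination cycle. The study team then decides whether to continue, change or discontinue.

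For Phase II, Section 20.0 provides a board that looks at progress, safety and key efficacy data: "The DSMC will review the study annually and will make recommendations". It gives no toxicity boundary, and Section 19 contains no safety monitoring analysis. On timing, Section 10.2 says of pembrolizumab events: "These adverse events may occur shortly after the first dose or several months after the last dose of treatment".

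**The concern.** Six patients followed for three weeks carry little information about a toxicity rate. The plan anticipates 0 or 1 event and stops at 2, so a single event separates the expected result from the stopping result. Once the lead-in is over, no count applies to the remaining patients: at least 27 − 6 = 21 evaluable, and up to 41 − 6 = 35 enrolled. Immune-related events that appear after the first cycle fall outside the only count there is.

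What is at stake is whether an excess toxicity rate that the first six patients happened not to show would be recognised promptly, against a threshold agreed in advance. As written, recognition depends on someone judging the accumulated events to be too many.

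**Working it through.** **The plan's own figures.** No operating characteristic is stated for the safety rule, so there is none to reproduce. The stated design figures concern efficacy: 4 or more responders in 27, null 0.05, alternative 0.20. Exact binomial gives an error of 0.0437 and power of 0.818, consistent with the stated 5% and 80%. They are not in dispute.

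**Inputs from the documents.** Lead-in of 6 and trigger at 2 or more (Sections 9.1, 19.1); 3-week cycle (10.0); 27 evaluable (19.1); maximum enrolment 41 over 5 years (7.0).

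**Assumption.** The true rate p is not given in the documents, so a range is shown. Patients are taken as independent with a common p.

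**Lead-in rule.** P(silent) = P(X ≤ 1), X ~ Binomial(6, p), which equals (1−p)^6 + 6p(1−p)^5.

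| True rate p | (1−p)^6 | 6p(1−p)^5 | Silent | Triggers |
|---|---|---|---|---|
| 1/6 | 0.335 | 0.402 | 73.7% | 26.3% |
| 25% | 0.178 | 0.356 | 53.4% | 46.6% |
| 30% | 0.118 | 0.303 | 42.0% | 58.0% |
| 1/3 | 0.088 | 0.263 | 35.1% | 64.9% |
| 40% | 0.047 | 0.187 | 23.3% | 76.7% |

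**Effect of the word *unexpected*.** The table assumes that every limiting toxicity counts. Suppose instead that only a share u qualifies as unexpected (u is an assumption); p is then replaced by u × p. At p = 30%, the rule is silent 59% of the time for u = 75%, 78% for u = 50% and 93% for u = 25%.

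**Carrying the count forward.** Keep 2 of 6 and add looks at 5 of 12, 6 of 18 and 8 of 24, counting first-cycle events in combination-treated patients. An exact recursion follows the distribution of the running count and removes at each look the paths that have reached the boundary.

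| True rate p | Lead-in only | With added looks | Gain | Caught among trials that pass the lead-in |
|---|---|---|---|---|
| 1/6 | 26.3% | 28.5% | 2.2 points | 3% |
| 30% | 58.0% | 71.0% | 13.0 points | 31% |
| 1/3 | 64.9% | 79.7% | 14.8 points | 42% |

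The last column is gain ÷ P(silent at lead-in); at 1/3, 14.8 / 35.1 = 42%, so about 58% of such trials would still not trigger. At 1/3 the gain splits into 2.8 points at 12 patients, 8.7 at 18 and 3.3 at 24.

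**Frequency of annual review.** 41 / 5 = 8.2 enrolled per year; 27 / 5 = 5.4 evaluable per year.

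**The case against.** Three stronger readings are tempting, and the documents support none of them.

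- *A 30% toxicity rate would enter Phase II 42% of the time.* The 42% is only the chance that the automatic count stays silent. Section 9.1 suspends the study for a judgement review whatever the count, and Phase II starts only after a safe treatment plan has been settled. The chance of entering Phase II cannot be computed.
- *The sponsor's own rule marks 30% or 1/3 as unacceptable.* The plan stops on an observed 2 of 6. It never states a true rate that would be too high.
- *Nothing but the annual review protects later patients.* Appendices F and J hold numeric patient-level hold and discontinuation criteria. Events of clinical interest are reported within 24 hours (17.4), and serious events and unanticipated problems within 1 business day (17.6, 17.8). Section 18.4 allows immediate termination for safety. Section 17.8 even lets an unexpected frequency count as an unanticipated problem. These are real controls, but none fixes a cumulative rate at which the study pauses.

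The added looks can also be criticised. They come six patients apart, which is not much more often than a yearly review at 5 to 8 patients a year. Most of the gain arrives at 18 patients, when two thirds of 27 have been treated. The 5-of-12 boundary (42%) is itself lenient. They count first-cycle events only, so they do nothing about late toxicity. All of this stands. It limits how much the change can achieve, but a threshold agreed in advance still adds something that open-ended review lacks. A single-arm trial with a safety lead-in and board review is a legitimate design choice; the point is an improvement to it.

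**Conclusion.** The concern holds in a limited form. The 2-of-6 check is the only study-level toxicity count, it discriminates weakly over plausible rates, and no cumulative guideline follows it. The silent probabilities rest on assumed true rates and on every limiting toxicity being counted; under the narrower *unexpected* wording they are higher. The mismatch between that wording and the dose-limiting toxicity definition is an inconsistency in its own right, and it leaves unclear which event any count would use.

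The benefit of carrying the count forward is moderate: about 13 to 15 points more chance of a trigger at true rates of 30% to 1/3. It is worth doing because it is cheap and concerns patient safety. It is an addition to the existing safeguards and does not imply that the trial is unmonitored.

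**What to change.** 1. In Sections 9.1 and 19.1, reconcile the stopping rule's wording with the dose-limiting toxicity definition so that one stated event is counted. Which event that should be is for the sponsor to decide.
2. In Sections 19.1 and 20.0, carry that count forward to all combination-treated patients as a guideline that pauses new starts and refers the data to the board, for example at 5 of 12, 6 of 18 and 8 of 24, with the lead-in rule kept. State its operating characteristics over a range of true rates. If the sponsor has an unacceptable rate in mind, name it and set the boundaries to it.
3. Because these looks cover the first cycle only, give the board at each review a cumulative tabulation of later treatment-related grade 3 or higher events.

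The cost is about a paragraph of text, using adverse event data already collected, and about 2 points more chance of an unnecessary pause if the true rate is 1/6 (28.5% against 26.3%). No dose or patient-level management rule changes.
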